### **9.2.1. Pregnancy**

Female subjects of child-bearing potential will have urine pregnancy tests conducted at baseline (Day 1) visit and at the unscheduled visits, if needed. Only subjects with negative pregnancy test results will be enrolled. Any subjects with positive pregnancy test results at any time during the study will be presented in a listing.

### **9.2.2. Events of Clinical Interest**

The frequency and percentage of subjects with the following elevations will be summarized at any post-baseline visit:

- ALT or AST  $> 8 \times$  the upper limit of normal (ULN);
- ALT or AST  $> 5 \times$  ULN for more than 2 weeks or accompanied by total bilirubin  $> 2 \times$  ULN.

A listing will be provided for the above elevations, including the actual measurement of ALT, AST, and total bilirubin, and their reference high limits.

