14.12 Sample Collection for Safety Laboratory Tests

Safety laboratory tests will be performed by a qualified central laboratory. Blood samples for safety laboratory tests will be collected at the Days -4 to -2 visit (Acute Phase, lab visit only) to determine subject eligibility. Lab results will be reviewed at Baseline (Day 1). Additional samples will be collected at Week 12 and at unscheduled visits, if needed. If indicated, these may be done at Week 36 to follow up on a laboratory abnormality.

The following laboratory parameters will be determined:

Hematology

- White blood cell (WBC) count
- Red blood cell (RBC) count
- Platelet count
- Differential WBC count will include percentages for lymphocytes, monocytes, eosinophils and basophils, and absolute counts for neutrophils, lymphocytes, atypical lymphocytes, monocytes, eosinophils and basophils.
- Hemoglobin
- Hematocrit

Blood Chemistry

- Glucose
- Hemoglobin A1C (glycosylated hemoglobin)
- Albumin
- Sodium
- Potassium
- Alkaline Phosphatase
- Creatinine
- Blood Urea Nitrogen (BUN)
- Total creatine phosphokinase (CPK)
- Aspartate aminotransferase (AST/SGOT)
- Alanine aminotransferase (ALT/SGPT)
- Gamma glutamyl transferase (GGT)
- Bilirubin (total, direct and indirect)
- Total protein

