16.3 Events of Clinical Interest

The following are considered events of clinical interest (ECIs) if they occur after dosing, and must be reported by the site when it becomes aware of the ECI:

- ALT or AST $> 8 \times$ the upper limit of normal (ULN), confirmed by repeat testing
- ALT or AST $> 5 \times$ ULN for more than 2 weeks or accompanied by total bilirubin $> 2 \times$ ULN

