#### 4. General Statistical Considerations

Continuous data will be described using descriptive statistics (i.e. n, mean, standard deviation (SD), median, minimum, and maximum). Categorical data will be described using the subject count and percentage in each category. For the summary statistics of all numerical variables unless otherwise specified, minimum and maximum will be displayed to the same level of precision as reported. Mean and median will be displayed to one level of precision greater than the data collected. Standard deviation / standard error will be displayed to two levels of precision greater than the data collected. P-values will be rounded to three decimal places. If a p-value is less than 0.001 it will be reported as “<0.001.” If a p-value is greater than 0.999 it will be reported as “>0.999.” Data will be displayed in all listings sorted by treatment group.

Subjects will be identified in the listings by the subject identification number concatenated with the investigator number.

When count data are presented, the percentage will be suppressed when the count is zero in order to draw attention to the non-zero counts. A row denoted “Missing” will be included in count tabulations where specified on the shells to account for dropouts and missing values. The denominator for all percentages will be the number of subjects in that treatment within the analysis set of interest, unless otherwise specified.

Unless otherwise specified, baseline will be defined as the last non-missing assessment prior to or on the date (and time if appropriate) of the first dose of study drug. Change from baseline is defined as post-baseline value – baseline value.

The study day will be calculated as follows:

If the assessment date occurs on or after the date of the first dose of study drug:

$$\text{Study day} = \text{assessment date} - \text{first dose date} + 1.$$

If the date of interest occurs before the date of the first dose of study drug:

$$\text{Study day} = \text{assessment date} - \text{first dose date}$$

There is no study day 0.

All analyses will be conducted using SAS Version 9.3 or higher. All statistical tests will be two-sided and interpreted at a 5% significance level.

This statistical analysis plan is created for the main study. Regarding the detailed description of the statistical analysis of the nested sub-study, please refer to the [Appendix 4](#).

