#### **11. Changes in the Planned Analysis**

The following have changed from the protocol:

- For the continuous efficacy endpoints except for the absolute number of Mycologically Proven, Presumed or Suspected Recurrences from Baseline (Day 1) to Week 24 (TOC) and Week 36 (EOFU), a Mixed-Effect Model for Repeated Measure (MMRM) analysis model and an analysis of covariance (ANCOVA) model are recommended rather than a two-way ANOVA model. Baseline value will be considered as possible contributor to any observed differences. Additionally, other variables may be considered during blinded data review.
- Add the randomization stratification factor, uncontrolled diabetes mellitus (Yes or No), as justification factor in the efficacy analyses models.

- For efficacy analyses, Country is recommended rather than site to be used as the justification factor.
- In protocol, it stated that the safety and tolerability as measured by AEs, vital signs, treatment discontinuation and safety laboratory tests at TOC (Week 24). The texts “at TOC (Week 24)” is removed since all safety data captured in this study will be taken into account for analysis.
- Intent-to-treat (ITT) Set definition was changed to be “All randomized subjects who signed the consent form and received at least one dose of study drug (ibrexafungerp or placebo).”
- Modified Intent-to-treat (mITT) Set definition was changed to be “All randomized subjects who signed the consent form and received at least one dose of study drug (ibrexafungerp or placebo), who have a confirmed mycological culture for yeast at Screening and a negative culture for yeast at Baseline (Day 1).”
- The number of recurrence episodes will be classified to 4 order categories for analysis rather than 3 categories as mentioned in the protocol. Updated based on client’s request.

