#### **13.4.9.2.2. Events of Clinical Interest**

The frequency and percentage of subjects with the following elevations will be summarized at any post-baseline visit:

- ALT or AST  $> 8 \times$  the upper limit of normal (ULN);
- ALT or AST  $> 5 \times$  ULN for more than 2 weeks or accompanied by total bilirubin  $> 2 \times$  ULN.

A listing will be provided for the above elevations, including the actual measurement of ALT, AST, and total bilirubin, and their reference high limits.

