#### **13.4.11. Changes in the Planned Analysis**

For the clinical failure definition, the texts “less than 50% reduction from baseline in the total composite VSS score” was used to replace “persistence and/or worsening of signs and symptoms” we have in the protocol.

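### The SAP's Events of Clinical Interest tables count ALT/AST above 8 × ULN without the repeat-test confirmation that the protocol requires, and neither SAP list of changes says so

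*SAP*

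**What the plan says.** **Protocol.** Sections 16.3 and 21.3.12.2 give the same two ECI criteria for the main study and the nested sub-study. The first is ALT or AST above 8 × "the upper limit of normal (ULN), confirmed by repeat testing". The second is ALT or AST above 5 × ULN that either lasts more than 2 weeks or comes with total bilirubin above 2 × ULN. Sites must report an ECI when they become aware of it.

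**SAP.** Sections 9.2.2 and 13.4.9.2.2 carry the same heading as the protocol sections. Both say: "The frequency and percentage of subjects with the following elevations will be summarized at any post-baseline visit". The first row is ALT or AST above 8 × ULN with no further condition. The second row repeats the protocol: above 5 × "ULN for more than 2 weeks or accompanied by total bilirubin" above 2 × ULN. Each section then adds a listing limited to those rows: "A listing will be provided for the above elevations".

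**Lists of changes.** SAP 11 opens with "The following have changed from the protocol" and has seven bullets. One concerns safety (the Week 24 restriction is removed) and none concerns ECIs. SAP 13.4.11 has a single entry, which begins "For the clinical failure definition".

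**Laboratory schedule.** In the main study, after the pre-randomization draw on Days -4 to -2, "Additional samples will be collected at Week 12 and at unscheduled visits, if needed" (Protocol 14.12), and Week 36 may be used to follow up an abnormality. In the sub-study the routine draw is Day 11, with others as needed (Protocol 21.3.10.13).

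**The concern.** One label, Event of Clinical Interest, has two definitions. Sites report under the confirmed one and the table counts under the unconfirmed one. The second criterion is the same in both documents, so a reader has reason to assume that the first was carried over too. Someone who takes the above-8 row as the protocol-defined count may read it too high, and nothing in the SAP warns of this. These two rows are the whole ECI table in each study.

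The second row has a different, operational weakness. Its duration limb needs repeated values, but each study schedules only one routine post-dose draw, and the SAP gives no rule for deriving duration. A moderately high value that was never usefully repeated would be missing from the table and the listing that are meant to draw attention to liver enzymes.

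**Working it through.** No figure in the plan needs reproducing. The check compares the two definitions case by case.

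**Inputs.** Let x be the peak post-dose ALT or AST in multiples of ULN. Let C mean that a repeat test confirmed a value above 8 × ULN, D that an elevation above 5 × ULN is shown to last more than 2 weeks, and B that total bilirubin is above 2 × ULN.

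- Protocol 16.3 and 21.3.12.2: ECI if (x > 8 and C) or (x > 5 and (D or B)).
- SAP 9.2.2 and 13.4.9.2.2: ECI if (x > 8) or (x > 5 and (D or B)).

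**Enumeration.** Take x as 6 or 9, C and D each as yes, no or unknown, and B as yes or no. That gives 2 × 3 × 3 × 2 = 36 combinations. They are logical cases, not probabilities.

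| Case | Combinations | Protocol | SAP |
|---|---|---|---|
| x = 9, C no or unknown, D no or unknown, B no | 2 × 2 × 1 = 4 | not an ECI | ECI |
| All other cases | 36 − 4 = 32 | same | same |

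**Step 1: direction.** In all four differing cases the SAP counts a subject whom the protocol does not. The reverse never occurs, so the SAP set contains the protocol set.

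**Step 2: row against subject.** The above-8 row on its own differs whenever x > 8 and C is not yes: 2 × 3 × 2 = 12 of the 18 combinations at x = 9. In 12 − 4 = 8 of these the subject is still a protocol ECI through D or B. So the row can be too high while the number of subjects with any ECI is unchanged.

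**Step 3: the second row.** At x = 6 the documents agree in all 18 combinations. With B yes, the value meets the second row whatever its duration. With B no and D unknown (3 × 1 × 1 = 3 combinations), it meets neither row under either document. This gap comes from the protocol definition, which the SAP copies.

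**Step 4: can D be known?** One routine post-dose draw cannot show duration, so D rests on as-needed repeats. The only follow-up visit that Protocol 14.12 names is Week 36, nominally 36 − 12 = 24 weeks after Week 12. A normal result then does not show whether the rise lasted 2 weeks. An unscheduled draw could, if taken in time.

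**Step 5: size.** The documents give no rate of ALT or AST above 5 × ULN. Each unconfirmed subject above 8 × ULN adds one to the row. How many there would be is unknown and may be zero.

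**The case against.** The strongest reply is that nothing planned was changed. Protocol 16.3 is a trigger for site reporting, and the protocol's safety analysis sections (18.7.2, 21.3.14.6.2) plan no ECI table. On that view SAP 9.2.2 is an added output that describes its rows as elevations, and SAP 11 had nothing to list. This is fair as far as it goes. But the SAP presents the rows under the ECI heading, and SAP 11 introduces its list as differences from the protocol at large. A reader still meets one name with two definitions.

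The second reply is that no signal is lost. This stands. The SAP can only over-count, its listing shows the actual ALT, AST and bilirubin values, and SAP 9.2 and 13.4.9.2 keep shift tables, extreme-value summaries and flagged listings. Safety is descriptive. These facts set the severity, but the other outputs do not label confirmation, so the protocol count would have to be rebuilt by hand.

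The third reply is that repeats are likely. An abnormality judged clinically significant is an AE (Protocol 16.1) and is followed to resolution or another outcome, even after participation ends (16.12, applied to the sub-study by 21.3.12.1). This also stands, and it narrows the second-row gap to values without an informative repeat. The table shells might help too: SAP 4 says that a row for missing data "will be included in count tabulations where specified on the shells to account for dropouts and missing values". The shells are not in the documents, and such a row would not restore the confirmation condition.

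A reader might go further and infer that the SAP hides liver signals, that it altered the above-5 criterion, or that every unconfirmed subject inflates the number of subjects with an ECI. The documents support none of these: the error runs towards over-counting, the above-5 wording matches the protocol, and Step 2 shows that many unconfirmed subjects remain protocol ECIs.

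**Conclusion.** The point holds and is minor. SAP 9.2.2 and 13.4.9.2.2 omit the confirmation condition for ALT or AST above 8 × ULN, and neither SAP 11 nor 13.4.11 says so. The above-8 row can exceed the protocol-defined count. The number of subjects with any ECI differs only for an unconfirmed value above 8 × ULN with bilirubin at or below 2 × ULN and no evidence of lasting more than 2 weeks. The direction is conservative and no formal inference is affected.

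Separately, a value above 5 and up to 8 × ULN, with bilirubin at or below 2 × ULN and no informative repeat, falls outside both ECI rows and the ECI listing. That is an operational gap inherited from the protocol, not a SAP departure, and the value remains in the general laboratory outputs.

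The conclusion rests on the wording alone. It assumes that the unseen table shells do not already separate confirmed from unconfirmed values. No percentage is given, because any event count would be arbitrary.

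**What to change.** In SAP 9.2.2 and 13.4.9.2.2, using data already collected:

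- **(a)** Split the above-8 row in two: confirmed by repeat testing, and not confirmed or not repeated. Define confirmed as the next repeat draw, within a stated window, also being above 8 × ULN. The documents give no window, so its length is a clinical choice to be fixed before unblinding in the main study and before full data review in the sub-study. Without one, a distant draw such as Week 36 could count as confirming Week 12.
- **(b)** Add one row for any post-dose ALT or AST above 5 × ULN regardless of duration, and include it in the ECI listing. Do not divide it into resolved within 2 weeks and longer. In the main study onset can fall anywhere between the pre-randomization draw and Week 12, so an early normal repeat does not show a short duration, and a subject with two episodes could fit both categories.
- **(c)** Note the difference from the protocol definition in SAP 11 and 13.4.11.

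The cost is SAP wording and one table shell per study, with no extra blood draw. The downside is a slightly longer table.

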## **9.3. Vital Sign Measurements**

Summary tables will be presented for vital sign data, including systolic blood pressure (mmHg), diastolic blood pressure (mmHg), body temperature ( $^{\circ}$ C), respiratory rate (bpm), and pulse rate (bpm), by treatment for subjects in the safety set. Observed results at the scheduled visits and

changes from baseline to the scheduled post-treatment visits will be presented. All vital sign data by subject will be presented in a listing.

#### **9.4. Abbreviated Physical Examination**

An abbreviated physical examination, including general appearance and an overall examination of body systems, will be conducted at Screening, Baseline (Day 1), Week 12 and Week 24 (TOC). Abbreviated physical exams may also be conducted at unscheduled visits, if needed.

The abbreviated physical examinations will be classified as Normal, and Abnormal at baseline. The post-baseline examinations will be classified as “Changes from baseline” or “No change from baseline”. This categorical data will be summarized with the frequency and percentage of subjects by body system at each scheduled visit.

All abbreviated physical examination data will be presented in a listing for all subjects.

#### **9.5. Vaginal Samples – pH, KOH and Other Pathogen Results**

Please refer to the section 14.7 of the protocol for the details of the Vaginal samples collection.

The KOH testing results will be classified as Positive (Yeast Only), Positive (Yeast and other pathogens), Negative (Yeast and other pathogens), and Positive (Other pathogens only). This categorical data will be summarized with the frequency and percentage of subjects at the scheduled post-baseline visits by treatment group.

The proportion of subjects with Chlamydia, Gonorrhea, and Herpes will be summarized at the scheduled visits by treatment group.

All vaginal sample testing data will be presented in a listing.

#### **10. Interim Analysis**

No interim analysis is planned for this study.

#### **11. Changes in the Planned Analysis**

The following have changed from the protocol:

- For the continuous efficacy endpoints except for the absolute number of Mycologically Proven, Presumed or Suspected Recurrences from Baseline (Day 1) to Week 24 (TOC) and Week 36 (EOFU), a Mixed-Effect Model for Repeated Measure (MMRM) analysis model and an analysis of covariance (ANCOVA) model are recommended rather than a two-way ANOVA model. Baseline value will be considered as possible contributor to any observed differences. Additionally, other variables may be considered during blinded data review.
- Add the randomization stratification factor, uncontrolled diabetes mellitus (Yes or No), as justification factor in the efficacy analyses models.

- For efficacy analyses, Country is recommended rather than site to be used as the justification factor.
- In protocol, it stated that the safety and tolerability as measured by AEs, vital signs, treatment discontinuation and safety laboratory tests at TOC (Week 24). The texts “at TOC (Week 24)” is removed since all safety data captured in this study will be taken into account for analysis.
- Intent-to-treat (ITT) Set definition was changed to be “All randomized subjects who signed the consent form and received at least one dose of study drug (ibrexafungerp or placebo).”
- Modified Intent-to-treat (mITT) Set definition was changed to be “All randomized subjects who signed the consent form and received at least one dose of study drug (ibrexafungerp or placebo), who have a confirmed mycological culture for yeast at Screening and a negative culture for yeast at Baseline (Day 1).”
- The number of recurrence episodes will be classified to 4 order categories for analysis rather than 3 categories as mentioned in the protocol. Updated based on client’s request.

### 13. Appendices

#### 13.1. Appendix 1: Schedule of Assessments

Study Week/Day  Study Procedures	Screen a  D -16 to -14	Acute Phase (Days -14 to -1 [+3 d])			Prevention of Recurrence										Unsch c
		D-14 a	D -11 & -8 Phone	D -4 to -2 Lab	Study Treatment Period (D1 to W24)							Follow-up Period (W25 to W36)			
					W1/ D1 (BL)	W4/ D28 (±3 d)	W8/ D56 (±3 d)	W12/ D84 (±3 d)	W16/D112 Phone b	W20/D140 Phone b	W24/ D168 (TOC) (±3 d)	W28 & W32 Phone b	W36 (EOFU) (±3 d)		
Informed Consent	X														
Assignment of Subject ID number	X														
Inclusion/exclusion criteria	X				X										
Medical history and demographics	X														
Abbreviated physical exam	X				X			X			X				If needed
Urine pregnancy test	X				X										If needed
Vulvovaginal sample for KOH d	X					If PR e	If PR e	If PR e			If PR e		If PR e	If PR e	
Vulvovaginal sample for fungal culture d	X				X	If PR e	If PR e	X			X		X	If PR e	
Vulvovaginal sample for pH d	X				X	If PR e	If PR e	If PR e			If PR e		If PR e	If PR e	
Vulvovaginal sample for other pathogens d	X					If PR e	If PR e	If PR e			If PR e		If PR e	If PR e	
Vulvovaginal exam f and rating of signs by the investigator	X				X	If PR e	If PR e	X			X		If PR e	If PR e	
Rating of vulvovaginal symptoms by the subject g	X	X-----X			X-----X										X
Open-label FLU dispensing		X													
Open-label FLU dosing h		X	X												
Subject diary dispensing and collection		X			X			X			X		X		
Subject diary completion		X-----X													
Subject diary review					X	X	X	X			X		X	X	
Sample collection for safety labs (hematology and blood chemistry)				X i				X					X j	If needed	

Study Week/Day  Study Procedures	Screen a  D -16 to -14	Acute Phase (Days -14 to -1 [+3 d])			Prevention of Recurrence										Unsch c
		D-14 a	D -11 & -8 Phone	D -4 to -2 Lab	Study Treatment Period (D1 to W24)								Follow-up Period (W25 to W36)		
					W1/ D1 (BL)	W4/ D28 (±3 d)	W8/ D56 (±3 d)	W12/ D84 (±3 d)	W16/D112 Phone b	W20/D140 Phone b	W24/ D168 (TOC) (±3 d)	W28 & W32 Phone b	W36 (EOFU) (±3 d)		
Open-label FLU collection and compliance evaluation					X										
Assessment of clinical outcome to FLU treatment					X k										
Randomization					X										
Blinded study drug dispensing					X				X						
Blinded study drug dosing l					X	X	X	X	X	X					
Quality-of-life assessment m		X			X			X			X		X		
Assessment for potential recurrence						X	X	X	X	X	X	X	X	X	X
Blinded study drug compliance evaluation						X	X	X	X	X	X				
Blinded study drug collection								X			X				
Vital Signs	X	X			X	X	X	X			X		X	X	X
Prior & concomitant medication review	X	X	X		X	X	X	X	X	X	X	X	X	X	X
Adverse event monitoring	X	X	X		X	X	X	X	X	X	X	X	X	X	X

Abbreviations: BL = Baseline; d = day; D = Day; EOFU = end of follow-up; FLU = fluconazole; ID = identification; KOH = potassium hydroxide; Phone = Phone contact; PR = potential recurrence; Screen = Screening; TOC = test of cure; Unsch = unscheduled; VSS = vulvovaginal signs and symptoms; VVC = vulvovaginal candidiasis; W = Week;

**Note regarding visits:** Whenever possible, on-site visits and phone contacts will be scheduled to occur on the date of dosing (or as close to the date of dosing as possible) to facilitate reminding subjects to take their study doses. This is applicable for the Baseline (Day 1), Week 4, Week 8, Week 12, Week 16 (phone contact), and Week 20 (phone contact) visits. Phone contacts will be conducted to check for adverse events, treatment compliance, potential recurrence, and concomitant medication use, including other antifungal agents.

- Screening and Day-14 may occur on the same day.
- If there is suspicion of a potential recurrence, subjects will be strongly discouraged from self-administering any treatment and will be instructed to visit the study center for a proper evaluation of their recurrence before initiating any VVC treatment.
- Unscheduled visits should be conducted anytime that there are symptoms indicating a potential recurrence or an adverse event. If there is suspicion of a potential recurrence, subjects will be strongly discouraged from self-administering any treatment and will be instructed to visit the study center for a proper evaluation of

	Screen a	Acute Phase (Days -14 to -1 [+3 d])			Prevention of Recurrence									
		Study Treatment Period (D1 to W24)										Follow-up Period (W25 to W36)		Unsch c
Study Week/Day	D -16 to -14	D-14 a	D -11 & -8 Phone	D -4 to -2 Lab	W1/ D1 (BL)	W4/ D28 (±3 d)	W8/ D56 (±3 d)	W12/ D84 (±3 d)	W16/D112 Phone b	W20/D140 Phone b	W24/ D168 (TOC) (±3 d)	W28 & W32 Phone b	W36 (EOFU) (±3 d)	
Study Procedures														

their recurrence before initiating any VVC treatment.

- d. Vulvovaginal specimens will be obtained at the specified visits and anytime that a recurrence is suspected for local vaginal pH determination and KOH testing as well as to rule out bacterial vaginosis and *Trichomonas vaginalis* (wet-mount or other, process locally). Testing for *Neisseria Gonorrhoeae*, *Chlamydia trachomatis* or *Herpes* virus may also be conducted if these pathogens are suspected (central laboratory). Samples for fungal culture should also be collected for processing at a central laboratory. Susceptibility testing will be done centrally at Screening and for all positive cultures during the study.
- e. Only if there is suspicion of a potential recurrence.
- f. If a subject is actively menstruating at an on-site study visit that requires a vaginal exam, the visit should be rescheduled as soon as the subject’s period ends but in no case more than 7 days after the initially scheduled visit.
- g. From Baseline (Day 1) through the Week 36 (EOFU) visit, subjects will rate their symptoms and record their scores on the VSS Scale included in their subject diaries. Symptoms of infection will be rated on a weekly basis and at the time of each scheduled or unscheduled visit to the site.
- h. The first dose of fluconazole will be administered at the site on Day -14, after all other visit procedures have been done. The remaining doses will be self-administered by the subjects at home.
- i. Conducted by the central lab. Results will be reviewed at Baseline (Day 1).
- j. Only if needed to follow up on a lab abnormality
- k. If the subject has a culture-confirmed *Candida* spp. infection from the sample collected at Screening, achieves a significant resolution of all signs and symptoms of infection (total composite score  $\leq 2$  on the VSS Scale) and meets other eligibility criteria for the study, she will enter the Prevention of Recurrence Phase. Subjects who fail treatment with open-label fluconazole in the Acute Phase but continue to meet all other eligibility criteria will enter the open-label ibrexafungerp Nested Sub-Study (see [Section Error! Reference source not found.](#) [Appendix C]). Subjects who are not eligible for this study or the Nested Sub-Study will be discontinued.
- l. Oral ibrexafungerp or placebo administered as a single-day treatment repeated every 4 weeks (28 days  $\pm 3$ ) for a total of 6 single-day treatments (Baseline [Day 1], Week 4, Week 8, Week 12, Week 16 and Week 20). Each single-day treatment will consist of two doses of ibrexafungerp 300 mg each or placebo given 12 ( $\pm 4$ ) hours apart. Subjects will continue study drug treatment regardless of recurrence and/or administration of antifungal therapy. The first dose will be administered at the study site (Baseline [Day 1]) and the remaining doses will be self-administered by the subjects at home. Study drug should be administered preferably with or immediately after a meal.
- m. Quality of Life tools will include: Euro Quol 5 Dimensions (EQ-5D), Short Form Health Survey (SF-36) and Female Sexual Distress-Revised Scale (FSDS)

